7.0 Discontinuation of Study Treatment/Participation

7.1 Discontinuation of Study Treatment

Subjects may discontinue study medication at any time at his/her own request or may be discontinued at the discretion of the investigator for safety, behavioral, or compliance reasons.

Subjects must discontinue study medication for the following reasons:

- Recurrence of leukemia after a response
- Failure to achieve (or maintain) CR, CRh or CRI post-Chemotherapy Cycle 2
- Death
- Withdrawal of consent
- An AE or intercurrent illness that precludes further administration of protocol therapy or participation in the study
- Need for, or use of a prohibited concomitant medication
- Hematopoietic stem cell transplantation
- Pregnancy

If study treatment is permanently discontinued for any reasons, subjects shall remain in the study for long-term follow-up. See [Table 7](#) for assessments required for the End-of-Treatment evaluation and long-term follow-up.

7.2 Discontinuation from the Study

Subjects may withdraw from the study at any time at his/her own request or may be withdrawn at the discretion of the investigator for safety, behavioral, or compliance reasons. Subjects must discontinue study participation for the following reasons:

- Death
- The study is terminated by the Sponsor

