All subjects who achieve morphologic CR, CRh, or CRi upon completion of Chemotherapy Cycle 2 may initiate or continue consolidation therapy in combination with ENTO or placebo (in accordance with their original randomized treatment assignment), as outlined in [Table 5](#) at the investigator's discretion either instead of or as a bridge to hematopoietic stem cell transplant.

Table 5: Treatment Phase –Consolidation

	Age < 60 years	Age \geq 60 years
Cytarabine	3.0 g/m ² , BID over 3 hours on Days 1, 3 and 5 every 28-35 days for up to 3 cycles*	1.5 g/m ² , BID over 3 hours on Days 1, 3 and 5 every 28-35 days for up to 3 cycles*

For subjects with < 5% residual blasts post-Induction Cycle 1, Consolidation Cycle 1 will consist of Chemotherapy Cycle 2. For patients with \geq 5% residual blasts post-Induction Cycle 1, Induction Cycle 2 ([Table 4](#)) will consist of Chemotherapy Cycle 2 with consolidation beginning thereafter. All subjects are eligible to receive up to 3 cycles of high dose cytarabine after Chemotherapy Cycle 2.

All subjects will undergo an End-of-Study Treatment Visit 30 ± 7 days after the last study treatment (either ENTO/placebo or chemotherapy, whichever is later) or prior to initiation of follow-on therapy (eg, maintenance therapy, HSCT), if sooner than 30 ± 7 days after last study treatment.

All subjects regardless of their post-remission status will be followed monthly for 3 months after the End-of-Study Treatment Visit and thereafter at least once every 3 months for progression/relapse, first salvage therapy, and survival until study termination. Unscheduled study visits at other time points are permitted in the setting of suspected leukemic recurrence or for evaluation and management of post-treatment sequelae.

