7.3 Lost to Follow up

A participant will be considered lost to follow-up if he or she repeatedly fails to return for scheduled visits and is unable to be contacted by the study site.

The following actions must be taken if a participant fails to return to the clinic for a required study visit:

The site must attempt to contact the participant and reschedule the missed visit as soon as possible and counsel the participant on the importance of maintaining the assigned visit schedule and ascertain whether or not the participant wishes to and/or should continue in the study.

Before a participant is deemed lost to follow up, the investigator or designee must make every effort to regain contact with the participant (where possible, telephone calls and, if necessary, a certified letter to the participant's last known mailing address or local equivalent methods). These contact attempts should be documented in the participant's medical record.

CONFIDENTIAL

Protocol KB-ENTO-3001 v4.0 Global
(Amendment 3.0 Global)

Should the participant continue to be unreachable, he/she will be considered to have withdrawn from the study.

CONFIDENTIAL

Protocol KB-ENTO-3001 v4.0 Global
(Amendment 3.0 Global)

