9.4.3 Secondary Endpoint(s)

The secondary endpoint variables and their population level summary measures will be described in each of the following sections. The evaluation of the population for the trial, treatments of interest, and the possible intercurrent events are as described in [Section 9.4.2.1](#). All secondary endpoints will include death as part of definition of the variable. Intercurrent events of additional leukemic therapy and premature study treatment discontinuation will be ignored for the primary evaluation of these endpoints. Additional information on the handling of missing data and sensitivity analyses will be detailed in the SAP.

CONFIDENTIAL

Protocol KB-ENTO-3001 v4.0

(Amendment 3.0)

Event-free survival

Event-free survival (EFS) is defined as time from randomization to the earliest of induction treatment failure (ITF), relapse for those who achieve CR, or death from any cause. ITF is failure to achieve morphological CR after completion of the last cycle of induction chemotherapy (no later than Day 42 of the last cycle of induction). Subjects who experience ITF will be treated as events at Day 1.

Subjects who do not experience an event (ITF, relapse from CR, or death) will be censored at their last study evaluation at which they were relapse free. Event-free survival will be estimated using the method of Kaplan-Meier (K-M) and summarized by treatment group. Differences between the treatment groups will be assessed with the log rank test stratified by age (<60 vs \geq 60 years) and choice of anthracycline in induction (daunorubicin vs idarubicin). The population level summary measure will be the adjusted hazard ratio as calculated from a Cox proportional hazards model with effects for treatment, age, and choice of anthracycline in induction.

Relapse free survival

For subjects who achieve CR, relapse free survival (RFS) is defined as the time from CR to morphologic relapse as assessed by the study site investigator or death from any cause, whichever comes first. Subjects who do not experience a relapse or death will be censored at the last study evaluation at which they were relapse free. RFS will be estimated using the K-M method and summarized by treatment group. The population level summary measure will be the adjusted hazard ratio as calculated from a Cox proportional hazards model with effects for treatment, age, and choice of anthracycline in induction.

Overall survival

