6. Acute coronary syndrome: administer aspirin to all subjects, regardless of platelet count. Individualize therapy based on cardiology consultation (patient may need to discontinue study participation after discussion with medical monitor).

CONFIDENTIAL

Protocol KB-ENTO-3001 v4.0
(Amendment 3.0)

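### Protocol Section 7.2 lets the investigator end a subject's study participation on the same grounds that Section 7.1 uses to stop study medication only, so follow-up that the intention-to-treat analyses need can be lost

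*Protocol*

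**What the plan says.** Two adjacent sections of the protocol give the investigator the same discretion with different consequences.

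- **Section 7.1 (treatment).** A subject "may be discontinued at the discretion of the investigator for safety, behavioral, or compliance reasons". The section ends with a mandatory rule: "If study treatment is permanently discontinued for any reasons, subjects shall remain in the study for long-term follow-up".
- **Section 7.2 (study).** A subject "may be withdrawn at the discretion of the investigator for safety, behavioral, or compliance reasons". No relapse or survival follow-up is required afterwards, and there is no threshold or medical-monitor step.

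Other passages bear on the point:

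- Section 4.1 describes follow-up for relapse, salvage therapy and survival without exception: "All subjects regardless of their post-remission status will be followed monthly for 3 months after the End-of-Study Treatment Visit", then at least every 3 months.
- Appendix 8 item 6, on acute coronary syndrome, notes in parentheses that the "patient may need to discontinue study participation after discussion with medical monitor".
- Section 9.4.3 sets the strategy for EFS, RFS and OS: "Intercurrent events of additional leukemic therapy and premature study treatment discontinuation will be ignored for the primary evaluation of these endpoints". Subjects without an event are censored at the last relapse-free evaluation for EFS, and at last contact for OS.
- Section 9.4.2.2 imputes a missing MRD result after Chemotherapy Cycle 2 as a failure.
- Section 9.4.2.1 names death, additional leukemic treatment and premature drug discontinuation as intercurrent events. It does not mention withdrawal from the study by the investigator.

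**The concern.** Safety and compliance problems are reasons to reconsider the drug. They are not in themselves reasons to stop recording whether a subject relapses or dies, because recording that needs no further exposure. With identical grounds in both sections, a site that uses 7.2 acts within the protocol and yet defeats the follow-up rule in 7.1.

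The analysis set is everyone randomized (Section 9.3), and ignoring treatment discontinuation works only if outcomes after discontinuation are observed. A 7.2 withdrawal replaces those outcomes with censoring. If the reason for withdrawal is related both to treatment and to prognosis, that censoring is informative. The primary endpoint is affected differently: the subject stays in the denominator, but an unobserved result is scored as a failure, which lowers the rate in whichever arm has more early withdrawals.

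**Working it through.** **1. Does the text separate the two routes?**

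| | Section 7.1 | Section 7.2 |
|---|---|---|
| Who decides | investigator (or subject) | investigator (or subject) |
| Grounds | safety, behavior, compliance | the same three |
| What ends | study medication | study participation |
| Follow-up afterwards | mandatory | none stated |

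It does not.

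**2. What each endpoint does with a subject withdrawn under 7.2**

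- EFS, no event recorded: censored at the last relapse-free evaluation.
- OS: censored at last contact.
- MRD negative CR, if the subject leaves before the post-Cycle 2 marrow: imputed failure. Section 9.5.3 expects such exits, because its analysis trigger counts subjects who leave before the assessment.

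**3. The plan's own power figure**

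Inputs from Section 9.2: 90 per group, 70% vs 42%, two-sided alpha 0.05. I used the normal approximation with pooled variance under the null:

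power = Φ[(d − 1.96 × SE0) / SE1]

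- d = 0.70 − 0.42 = 0.28, and the pooled rate is 0.56
- SE0 = √(0.56 × 0.44 × 2/90) = 0.0740
- SE1 = √((0.70 × 0.30 + 0.42 × 0.58)/90) = 0.0710
- power = Φ[(0.28 − 0.1450)/0.0710] = Φ(1.90) = 0.971

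This reproduces the stated figure of more than 97%.

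**4. Size on the primary endpoint (assumed range)**

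The documents give no study-withdrawal rate. Up to 10% over-enrollment is allowed, but for technical or logistical difficulty in obtaining MRD status in subjects with CR. I assume that k of 90 ENTO subjects leave before the assessment, that each would have succeeded with probability 0.70, and that placebo stays at 42%:

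ENTO rate = 0.70 − k × 0.70/90

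| k | ENTO rate | Difference | Power |
|---|---|---|---|
| 0 | 70.0% | 28.0 points | 97.1% |
| 3 | 67.7% | 25.7 points | 94.0% |
| 5 | 66.1% | 24.1 points | 90.7% |
| 8 | 63.8% | 21.8 points | 83.9% |

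Losses in both arms cost less. At 10% in each arm the rates are 63.0% and 37.8%, and power is 0.929. At 10% in ENTO only, the rates are 63.0% and 42%, and power is 0.811.

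**5. EFS**

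Section 9.2 plans 124 events for a hazard ratio of 0.6. Schoenfeld's approximation, Φ[√(124/4) × |ln 0.6| − 1.96], gives 0.812 against the stated 80%. If 10% of the events were lost and not replaced (111.6 left), power would be 0.770. Section 9.5.4 triggers the analysis on the event count, so the loss may appear first as delay. These figures measure lost information only. The bias from informative censoring cannot be computed from the documents.

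**The case against.** The strongest reply is that the specific rules already point to continued follow-up. The rash rule in Table 6 acts on study medication, the rule in 7.1 is mandatory, Section 4.1 covers all subjects, and 7.2 is only permissive. Read together, a careful site would keep following a subject with ordinary drug toxicity. This has force: it makes misuse less likely and shows what the authors probably intended. It does not remove the permission in 7.2, and nothing says that 7.1 prevails.

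Three further objections stand and limit the claim.

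- **Direction.** A reader might infer that withdrawals would remove sicker ENTO subjects and so flatter ENTO on EFS and OS while penalizing it on MRD. The documents do not support this. Nothing shows that ENTO toxicity predicts relapse or death. The trial is double-blind, which limits deliberate imbalance. It is also unsettled whether a subject who leaves before documented CR is censored or counted as an induction failure with an EFS event at Day 1; in the latter case EFS and the primary endpoint would move the same way.
- **Rate.** A reader might take the earlier study's Grade 3 or 4 rash (13%) and bilirubin (11%) as a guide to withdrawals. Those are toxicity rates. Section 6.8 says indirect bilirubin rises generally did not lead to stopping ENTO. Section 2.4 reports that rash improved to Grade 1 within 10 days of withholding ENTO, and that its one recurrence among four rechallenged subjects ended ENTO; it reports no exit from the study.
- **Appendix 8.** Item 6 is a parenthetical possibility after discussion with the medical monitor, and it concerns clinical management. It can be cited as inconsistent with 7.1, but this review should not rewrite it.

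Section 7.3, under which an unreachable subject is treated as withdrawn, is an ordinary loss-to-follow-up rule and adds nothing to the point.

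**Conclusion.** The conflict between 7.1 and 7.2 is real and worth correcting. A site that follows 7.2 as written ends the relapse and survival data on which the Section 9.4.3 strategy depends, and can turn an unobserved MRD result into a failure. The EFS and OS censoring may be informative, but its direction and size are not established.

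On the primary endpoint, the illustrative cost is 2.3 to 6.2 points off the ENTO rate (70% to between 67.7% and 63.8%) and a fall in power from 97% to between 94% and 84%. That range rests on three assumptions: 3 to 8 early withdrawals, all in the ENTO arm, and success at the planned 70% had they stayed. None comes from the documents. Scoring missing MRD as failure is pre-specified and, when the losses are in the ENTO arm, conservative for ENTO.

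The practical reach is limited. SAP Section 4.2 records 15 randomized subjects, and SAP Sections 6.4 and 8 drop the protocol-defined primary and secondary efficacy analyses. The point therefore applies to the protocol as designed, or as reused, and does not affect the abbreviated report.

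**What to change.** - In Section 7.2, remove investigator discretion for safety, behavior or compliance as a reason to end data collection. Limit study exit to withdrawal of consent for follow-up, loss to follow-up, death or study termination.
- State that after an investigator decision on those grounds, relapse and survival data continue to be collected where consent allows. The same should hold for the response and MRD assessment already scheduled after Chemotherapy Cycle 2, where it is still performed.
- Reconcile Appendix 8 item 6 with Section 7.1. Which clinical rule should apply there is for the sponsor to settle.

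The cost is protocol wording. The small downside is that sites keep contact with subjects they might otherwise have closed out. No additional drug exposure is involved.

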7.3 Lost to Follow up

A participant will be considered lost to follow-up if he or she repeatedly fails to return for scheduled visits and is unable to be contacted by the study site.

The following actions must be taken if a participant fails to return to the clinic for a required study visit:

The site must attempt to contact the participant and reschedule the missed visit as soon as possible and counsel the participant on the importance of maintaining the assigned visit schedule and ascertain whether or not the participant wishes to and/or should continue in the study.

Before a participant is deemed lost to follow up, the investigator or designee must make every effort to regain contact with the participant (where possible, telephone calls and, if necessary, a certified letter to the participant's last known mailing address or local equivalent methods). These contact attempts should be documented in the participant's medical record.

CONFIDENTIAL

Protocol KB-ENTO-3001 v4.0 Global
(Amendment 3.0 Global)

Should the participant continue to be unreachable, he/she will be considered to have withdrawn from the study.

CONFIDENTIAL

Protocol KB-ENTO-3001 v4.0 Global
(Amendment 3.0 Global)

8.0 Study Assessments and Procedures

The schedule of study assessments and procedures is summarized in [Table 7](#).

All study visits should be scheduled relative to the C1D1 date regardless of any treatment interruptions. Acceptable windows for study visits/assessments after C1D1 are \pm 1 day. Unscheduled study visits may be required as clinically indicated for evaluation of AEs or suspected leukemic relapse/progression. Results of diagnostic evaluations performed as part of an unscheduled study visit must be entered into the Unscheduled Visit eCRF.

CONFIDENTIAL

Protocol KB-ENTO-3001 v4.0
(Amendment 3.0)

Table 7: Schedule of Assessments and Procedures

Study Phase	Screening	Induction (up to 2 Cycles)*					At Recovery of Blood Counts/Assessment of Remission Status (Post-Induction Cycle 1, Post-Chemotherapy Cycle 2)/At Relapse	Consolidation (up to 3 Cycles)*				End-of-Study Treatment	Long-Term Follow-up ^x
Study Visit Day ^a	-14 to 0	1	3	7	14	15 until blood count recovery		1	3	5	28 to 35	30 ± 7 days after last study treatment	
Informed consent	X												
IxRS registration/randomization	X												
Medical/smoking history/prior medications/AML baseline characteristics ^b	X												
Safety assessments													
Vital signs ^c	X	X	X	X	X			X	X	X	X	X	
Physical examination ^d	X	X			X		X	X			X	X	
Height/weight ^e	X			X				X				X	
ECG ^f	X												
ECHO/MUGA ^g	X											X	
ECOG PS (Appendix 6)	X	X			X						X	X	
AEs/concomitant medications ^h	X	X	X	X	X			X	X	X	X	X	
Hematology ⁱ	X	X	X	X	X	X	X	X		X	X		
Clinical chemistries/LFTs ^j	X	X	X	X	X		X	X		X	X		
Coagulation ^k	X	X	X	X	X								
Urinalysis ^l	X												
β -HCG/FSH ^m	X	X						X				X	
HBV/HCV/HIV serologies ⁿ	X												

CONFIDENTIAL

Protocol KB-ENTO-3001 v4.0
(Amendment 3.0)

Study Phase	Screening	Induction (up to 2 Cycles)*				At Recovery of Blood Counts/Assessment of Remission Status (Post-Induction Cycle 1, Post-Chemotherapy Cycle 2)/At Relapse	Consolidation (up to 3 Cycles)*			End-of-Study Treatment	Long-Term Follow-up ^x
Study Visit Day^a	-14 to 0	1	3	7	14	15 until blood count recovery		1	3	5	28 to 35
Induction therapy											
Study medication (ENTO/Placebo) ^o						→	X				
Cytarabine				→							
Daunorubicin or Idarubicin			→								
Consolidation therapy											
Study medication (ENTO/Placebo) ^p								→			
Age-adjusted, high-dose cytarabine								→			
Bone marrow evaluations											
Aspirate ^q	X						X				
NPM1-m MRD assessments ^r	X						X			X	X
Pharmacokinetics ^s		X	X	X				X		X	
Peripheral blood biomarker assessments ^t	X	X	X	X			X	X		X	X
Bone marrow aspirate biomarker assessments ^u	X						X				
Pharmacogenomics (whole blood) ^v	X										
Patient reported outcomes ^w	X						X			X	X
Follow-up for relapse, first salvage therapy, OS ^x											X

CONFIDENTIAL

Protocol KB-ENTO-3001 v4.0
(Amendment 3.0)

Abbreviations: AEs, adverse events; AML, acute myeloid leukemia; β -HCG, beta human chorionic gonadotropin; ECG, electrocardiogram; ECHO, echocardiogram; ECOG PS, Eastern Cooperative Oncology Group Performance Status; FSH, follicle stimulating hormone; HBV, hepatitis B virus; HCV, hepatitis C virus; HIV, human immunodeficiency virus; LFTs, liver function studies; MUGA, multi-gated acquisition; *NPM1*-m, *Nucleophosmin 1*-mutated; MRD, measurable residual disease; OS, overall survival.

* Subjects with $\geq 5\%$ residual leukemic blasts in bone marrow aspirate between Days 14 and 28 of Induction Cycle 1 will receive Induction Cycle 2 as outlined in [Table 4](#), which may be administered prior to blood count recovery. Subjects who have achieved a complete response (CR) either with or without full hematologic recovery (CRh, CRi) or a morphologic-free leukemia state (MFLS) will proceed to Consolidation Cycle 1 ([Table 5](#)) upon recovery of peripheral blood counts (absolute neutrophil count [ANC] $\geq 1.0 \times 10^9/L$; platelet count $\geq 50 \times 10^9/L$). After completion of Induction Cycle 2 or Consolidation Cycle 1 (ie. Chemotherapy Cycle 2), subjects will undergo bone marrow examination for assessment of remission status at the investigative site. Patients in morphologic CR post-Chemotherapy Cycle 2 will undergo MRD assessment (see footnote "r" below).

^a Acceptable windows for study visits/assessments after C1D1 are ± 1 day; however, study treatment must be administered on the days indicated (eg, Days 1-7 for cytarabine, and Days 1-3 for daunorubicin or idarubicin in Induction Cycle 1).

^b The following details minimally, regarding the diagnosis of AML will be collected and recorded on the eCRF: age and date of diagnosis (month, day, year); AML subtype (*de novo*; AML with myelodysplasia-related changes; therapy associated AML); history of myelodysplastic or myeloproliferative (eg, chronic myelomonocytic leukemia [CMML]) syndrome; history of prior exposure to leukemogenic agents (eg, alkylating agents, topoisomerase II inhibitors); cytogenetic abnormalities identified by conventional cytogenetic testing and/or FISH; complete blood count (CBC) with differential; percent blasts (peripheral blood and bone marrow); *NPM1* mutation subtype (A, B, D, other); *FLT-3* mutational status (wild-type; internal tandem duplication [ITD] mutation, tyrosine kinase domain [TKD] mutation, or both).

^c Vital signs include measurement of blood pressure, respiratory rate, pulse, temperature, and oxygen saturation level by pulse oximetry. After discharge from hospital, assess vital signs at each of the designated time points.

^d Perform a complete physical examination including neurological exam at Screening. After discharge from the hospital, a targeted physical exam may be performed at each of the designated time points. Subjects ≥ 60 years old receiving intermediate dose cytarabine or those with impaired renal function are at risk for cerebellar toxicity. Monitor for the occurrence of nystagmus, slurred speech, or dysmetria on each day of cytarabine dosing during Induction Cycle 2 and consolidation. Follow dose modification guidelines outlined in [Section 6.5.2](#) or in accordance with institutional care standards in the setting of neurotoxicity.

^e Height and weight will be measured at Screening. Only weight will be measured thereafter at designated time points.

^f ECG is required at Screening and thereafter as clinically indicated during treatment.

^g An echocardiogram (ECHO) or multi-gated acquisition (MUGA) scan must be performed at Screening and at the End-of-Treatment Visit. Consider repeating ECHO or MUGA within 48 hours prior to Induction Cycle 2 for subjects receiving anthracycline in Cycle 2 and at increased risk for cardiac toxicity.

^h Record all adverse events and concomitant medications through 30 ± 7 days after treatment completion. Thereafter, record only serious adverse events assessed as study medication related.

ⁱ Includes hemoglobin, hematocrit, WBC and platelet counts, and WBC differential (neutrophils, bands, lymphocytes, monocytes, eosinophils, basophils, blasts). At times not designated in Table 7, monitor CBC and WBC differential in accordance with institutional care standards until ANC is $>1.0 \times 10^9/L$ or persistent leukemia is documented. Monitor platelet counts at times designated in Table 7 and at other times, per institutional care standards until the platelet count is $>100 \times 10^9/L$ or persistent leukemia is documented. Monitor CBC and platelet count twice weekly during consolidation and at other times, as clinically indicated.

^j Includes electrolytes (sodium, potassium, chloride, total CO₂ and/or bicarbonate, calcium, phosphate), liver function studies (aspartate aminotransferase [AST], alanine aminotransferase [ALT], total and direct bilirubin), lactate dehydrogenase (LDH), alkaline phosphatase, blood urea nitrogen [BUN] or serum urea, creatinine, uric acid, glucose, amylase, and lipase. Include total creatine phosphokinase (CPK) at Screening, Day 14 of each induction cycle, and End of Study Treatment. At times not designated in Table 7, monitor electrolytes, LFTs, BUN, creatinine, uric acid, and phosphate in accordance with institutional care standards until the risk of tumor lysis syndrome has abated. For subjects

CONFIDENTIAL

Protocol KB-ENTO-3001 v4.0
(Amendment 3.0)

receiving nephrotoxic antimicrobial agents, closer monitoring of renal function throughout the period of hospitalization is recommended, consistent with institutional standards of care.

^k Includes prothrombin time, activated partial thromboplastin time and international normalized ratio. Perform coagulation panel twice per week during Induction. For subjects with evidence of disseminated intravascular coagulation (DIC), coagulation parameters including fibrinogen should be monitored in accordance with institutional care standards until resolution.

^l Includes dipstick evaluation for pH, glucose, protein, blood, leukocyte esterase and microscopic evaluation for red and white blood cells. After Screening, perform urinalysis as clinically indicated.

^m A negative serum pregnancy test is required for female subjects (unless surgically sterile or postmenopausal) at Screening. Female subjects with medically documented ovarian failure must also have serum FSH levels within the institutional postmenopausal range at Screening. A urine pregnancy test will be performed for all females (unless surgically sterile or postmenopausal) on Day 1 of each cycle of induction and consolidation and at the End-of-Treatment Evaluation.

ⁿ HBV/HCV/HIV serology tests include HBsAg, anti-HBs, anti-HBc, anti-HCV, and anti-HIV.

^o Study medication will be administered orally every 12 hours during Induction Cycles 1 and Induction Cycle 2, if administered (see [Table 4](#)). Subjects are to continue receiving study medication while awaiting blood count recovery and response assessment results.

^p Subjects who achieve CR, CRh or CRi post-Chemotherapy Cycle 2 may receive **consolidation** chemotherapy in combination with study medication (see [Table 5](#)). Subjects are to continue receiving study medication while awaiting blood count recovery. The number of cycles of consolidation (up to 3) will be at the investigator's discretion.

^q A bone marrow aspirate will be performed at Screening (within 14 days before the first administration of study treatment) for confirmation of diagnosis, morphology (spicule prep), cytogenetics/FISH and *NPM1* and *FLT-3* mutational status. **In cases in which an adequate bone marrow aspirate cannot be obtained at Screening (eg, due to dry tap, hypocellularity or hemodilution), a trephine bone marrow biopsy is mandated.** Bone marrow aspirates are required in Induction Cycle 1 (up to but no later than Day 42) and again post-Chemotherapy Cycle 2 (no later than Day 42) to assess remission status. Thereafter, perform bone marrow examination for confirmation of suspected leukemic relapse.

^r *NPM1*-m allelic frequency will be assessed in peripheral blood and bone marrow aspirate in a central laboratory at the following time points: Screening; post-Chemotherapy Cycle 2 for subjects in CR (no later than Day 42, **for MRD assessment**); and at the End of Study Treatment visit (**peripheral blood only**). MRD will be assessed retrospectively on peripheral blood in subjects who achieve MRD negative CR post-Chemotherapy Cycle 2, every 3 months during long term follow-up until morphologic relapse.

^s Blood sampling for pharmacokinetic assessments will be performed at the following time points: **Cycle 1 (Induction):** Day 1 between 2- and 4-hours post-study medication dose, Day 7 predose only, Day 14 predose and between 2- and 4-hours post-study medication dose; **Cycle 3 (Consolidation):** Day 1 predose and between 2- and 4-hours post-study medication dose, Day 28-35 predose and between 2- and 4-hours post-study medication dose. All predose samples must be obtained within 60 minutes before the first daily dose of study medication ([Section 8.7](#)).

^t Blood samples for biomarker assessments including (but not limited to) other somatic mutations will be obtained at Screening; **Cycle 1 (Induction)**, Day 1 (predose and 2 hours post-dose), Day 7 and Day 14 (predose only) prior to the first daily dose of study medication; **Cycle 3 (Consolidation)** Day 1 (predose) and Day 28-35 (predose); at time of post-Chemotherapy Cycle 2; relapse; and End of Study Treatment. See [Section 8.9](#) for a description of planned biomarker assessments.

^u Bone marrow aspirate samples for biomarker assessments including (but not limited to) other somatic mutations will be obtained at Screening; post-Chemotherapy Cycle 2; and at relapse.

^v Whole blood will be collected during Screening for evaluation of CYP2C9 and cytidine deaminase polymorphisms. Examinations of other germline genes implicated in leukemogenesis may be conducted for comparison with corresponding genes in the leukemic clone. See [Section 8.9](#) for additional details.

^w Includes the European Quality of Life 5 Dimensions Questionnaire (EQ-5D-5L) and the European Organization for Research and Treatment of Cancer Quality of Life Questionnaire-Core 30 (EORTC-QLQ 30).

CONFIDENTIAL

Protocol KB-ENTO-3001 v4.0
(Amendment 3.0)

^x All subjects regardless of post-remission status will be followed monthly for 3 months after the End-of-Treatment Visit and thereafter at least once every 3 months for progression/relapse, first salvage therapy, and overall survival until study termination.

CONFIDENTIAL

Protocol KB-ENTO-3001 v4.0

(Amendment 3.0)

